# 9.0 ADVERSE EVENTS (AE)

All medical events, treatments and outcomes will be recorded in the subject's chart as per the site's routine medical practice but not all untoward medical events will be collected on the CRFs.

# 9.1 Protocol-defined Adverse Events

Adverse events as defined in this protocol include all ocular adverse events (AE) in the study eye. These events must be reported on the adverse event CRF. The Investigator must categorize each AE by degree of harm to the subject (mild, moderate, or severe), and the relationship to study device and implantation procedure (not related, possibly, probably, or definitely). Since there are no aspects of the study that can affect both eyes, only serious adverse events observed in the fellow eye will be captured on the case report form throughout the course of the study.

Ocular conditions or diseases that are chronic but stable and meet the inclusion and exclusion criteria should be recorded on the screening CRF under Ocular History. Changes in any chronic condition or disease that are consistent with natural disease progression are not considered AEs and will not be recorded on an AE CRF.

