# 4.0 STUDY DESIGN

This study is a post-market prospective, randomized, controlled, multicenter clinical trial in which a total of approximately 150 subjects will be randomized after successful cataract surgery to receive either the *Hydrus Implant* or the *iStent*. Potential study participants will be consented, at which time they will undergo screening criteria for eligibility. If eligibility criteria are met after initial screening, the study participants will undergo a screening washout phase during which all glaucoma medications (topical and oral) will be discontinued; the duration of the washout phase to be determined by the specific medication(s) used by the subjects. Following washout, the subjects will return for a baseline evaluation, and if found to continue to meet the eligibility requirements, and agree to participate, will be scheduled for cataract surgery, randomized, and followed up at specified intervals for a 2 year period. The study schema is presented in Figure 4.

Of the two eye implants being used in this study, the *HydrusTM Aqueous Implant* (the test article) is currently CE marked for use in the EU countries. It is intended for the reduction of intraocular pressure (IOP) in subjects with primary open angle glaucoma (POAG), pseudoexfoliative glaucoma, or pigmentary glaucoma as a stand-alone treatment or in conjunction with cataract surgery. The *iStent* (the control article) is currently CE marked for use in the EU countries. It is intended for the reduction of IOP in POAG subjects with concurrent cataract or in stand-alone treatment, and is thus considered a suitable control.

In the event a study subject does not respond to device therapy, hypotensive glaucoma medications may need to be prescribed during the follow up period to reduce IOP to a safe level, at the discretion of the attending physician. To address the confounding effect of medications on the assessment of the devices' ability to reduce IOP, a "wash-out" of all glaucoma medications will be conducted prior to the 12 and 24 month follow-up visits.

Figure 4: Study Schema

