After the subject has successfully completed the preoperative screening exam, he or she will be instructed to discontinue any ocular hypotensive medications in the designated treatment eye for the appropriate washout period, as listed in Table 2, *prior to* the Baseline Exam. If upon washout, the subject experiences an IOP spike of > 36 mmHg, or requires the reintroduction of hypotensive medications due to an IOP spike, or a surgical intervention during the preoperative period, the subject will be treated and will be considered for withdrawal from the study. However, sites should confirm with Ivantis if there are any questions.

TABLE 2         OCULAR HYPOTENSIVE MEDICATION WASHOUT PERIODS							
Carbonic Anhydrase Inhibitors							
Diamox ® (Acetazolamide) − oral Rx	14 days						
Neptazane® (Methazolamide) – oral Rx	14 days						
Azopt ® (Brinzolamide)	14 days						
Trusopt ® (Dorzolamide Hydrochloride)	14 days						
Alpha Adrenergic Agonist							
Alphagan ® (Brimonidine)	14 days						
Iopidine ® (Apraclonidine Hydrochloride)	14 days						
Beta Blockers							
Betagan ® (Levobunolol Hydrochloride)	28 days						
Betoptic ® (Betaxalol Hydrochloride)	28 days						
OptiPranolol® (Metipranolol)	28 days						
Timoptic/Betimol ® (Timolol Maleate)	28 days						
Prostaglandin Analogs							
Lumigan ® (Bimatoprost)	28 days						
Travatan ® (Travoprost)	28 days						
Xalatan ® (Latanoprost)	28 days						

TABLE 2 (Cont'd)         OCULAR HYPOTENSIVE MEDICATION WASHOUT PERIODS							
Combined Medications							
Combigan ® (Brimonidine Tartrate/Timolol Maleate)	28 days						
Cosopt ® (Dorzolamide Hydrochloride/ Timolol Maleate)	28 days						
Pilocarpine	7 days						
Dipivefrin and epinephrine products 28 days							

If subjects have not used any ocular hypotensive medications, they may be scheduled for a Baseline Visit up to 45 days after successfully completing the Screening Visit. At the Baseline Visit, upon confirmation of a successful washout, subjects will undergo an evaluation for continued eligibility.

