#### Safety Visit

Between the screening visit and the baseline visit, the subject's IOP status may be checked at the discretion of the investigator. Data from this visit will not be collected unless an adverse event occurs. If during the washout period, the subject experiences an IOP spike of > 36 mmHg requiring the use of hypotensive medication or surgical intervention, the subject will be exited from the study.

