#### 8.8 Treatment of the Fellow Eye

The fellow eye should be treated within the site's standard of care. Any enrolled subject – regardless of randomization assignment – may receive CE-marked *Hydrus Implant* treatment as part of the standard of care to the fellow eye in conjunction with planned IOL implantation – following initial randomization and treatment of the assigned eye in the study.

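### Section 9.1 limits fellow-eye adverse event capture to serious events on the premise that nothing in the study affects both eyes, but the study's washout of oral glaucoma drugs does

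*Combined protocol and SAP*

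**What the plan says.** Section 9.1 sets the scope of adverse event reporting by eye. For the study eye it is broad: "Adverse events as defined in this protocol include all ocular adverse events (AE) in the study eye". For the other eye it is narrow, and the reason is given in the same sentence: "Since there are no aspects of the study that can affect both eyes, only serious adverse events observed in the fellow eye" are to be entered on the CRF. Investigators then rate each event's relationship to two things only, the study device and the implantation procedure. Section 9.0 says that events are kept in the chart under routine practice, but that "not all untoward medical events will be collected on the CRFs".

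On washout, Section 4.0 says that at screening "all glaucoma medications (topical and oral) will be discontinued", and the Study Outline says the same. Table 2 in Section 8.1 gives the washout periods. It lists oral acetazolamide and "Neptazane® (Methazolamide) – oral Rx", at 14 days each. The instruction that introduces the table is worded for one eye: subjects are to "discontinue any ocular hypotensive medications in the designated treatment eye for the appropriate washout period". The Month 12 and Month 24 visit descriptions in Section 8.6 apply Table 2 again, where appropriate, to subjects who are on medication.

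Between Screening and Baseline, an optional Safety Visit may be held to check pressure. Of it the protocol says: "Data from this visit will not be collected unless an adverse event occurs".

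**The concern.** The serious-only rule for the fellow eye has a single stated justification, and that justification is absolute. If any part of the study reaches the fellow eye, the justification fails and the restriction has no stated basis.

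What is at stake is the completeness of the safety data. Washout is imposed by the study, and withdrawing a systemic pressure-lowering drug removes treatment from an eye that is not being operated on. Non-serious consequences in that eye would not appear among the trial's adverse events. Even if a site did report one, the form offers no way to attribute it to washout.

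**Working it through.** The plan gives no figure on this point, so the check is mainly a comparison of the texts.

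1. **The premise (Section 9.1).** No aspect of the study can affect both eyes. One counterexample is enough to defeat it.
2. **The counterexample (Study Outline, Section 4.0, Table 2).** Oral drugs are stopped, and two are named. Section 8.1 words the washout as applying to the treatment eye, but a systemic drug cannot be withdrawn from one eye. The wording in Sections 4.0, 8.1 and 9.1 needs to be reconciled.
3. **Recurrence (Section 4.0; Section 8.6, Months 12 and 24).** The Table 2 washout can occur up to three times: before Baseline, and before the Month 12 and Month 24 diurnal measurements.
4. **What the CRF captures before Baseline.** A non-serious fellow-eye event is not a protocol-defined adverse event, so it would not by itself trigger data collection at a Safety Visit. However, Appendix 1 starts scheduled adverse event assessment at surgery for either eye, so thin preoperative capture is not specific to the fellow-eye rule.
5. **What the CRF captures at Months 12 and 24.** Adverse event assessment is scheduled at these visits, so the Section 9.1 rule matters most here. One fellow-eye pressure reading is scheduled, but the visit text does not say whether it comes before or after a washout. The post-washout diurnal series is for the study eye.
6. **Where captured events go.** Section 6.3 plans frequency tabulations of safety outcomes. An event that stays in the chart does not reach the trial's adverse event counts.

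**Size.** The documents do not give the share of subjects on an oral agent. Purely as an assumption, take 2 to 10%:

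- Section 4.0, 150 randomized: 0.02 × 150 = 3 to 0.10 × 150 = 15 subjects.
- Section 8.1, 70 randomized: 0.02 × 70 = 1.4 to 0.10 × 70 = 7 subjects.
- Section 8.1, 100 enrolled, which is the relevant base for the preoperative washout because it precedes randomization: 0.02 × 100 = 2 to 0.10 × 100 = 10 subjects.

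The true share could be near zero. These counts should not be carried over to all three washouts. A postoperative washout applies only to subjects on medication at that time, and the investigator may decline it for safety reasons.

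**The case against.** The strongest reply is that little of importance is lost, and much of it stands.

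- **Fellow eyes are examined.** Baseline, which follows washout, includes fellow-eye tonometry, bilateral acuity and slit lamp examination, and an update of ocular history and medication in both eyes. Months 12 and 24 add bilateral visual fields and fundus examination. A reader might infer that fellow-eye effects go unrecorded altogether, or that the trial does not look. The documents do not support that. The gap is that non-serious events are not captured as adverse events on the CRF.
- **Serious events are captured.** The definition in Section 9.7 extends to events needing intervention to prevent a serious outcome. The preoperative rule on pressure spikes above 36 mmHg refers to the subject, not to one eye.
- **A pressure rise off treatment may not be an adverse event in either eye.** Entry requires a washed-out study-eye mean of 22 to 36 mmHg, so raised pressure is expected. The pressure item in Section 9.4 requires a mean at least 10 mmHg above the qualifying baseline, more than 1 month after surgery. This narrows the set of missed events. It does not empty it, because Section 9.2 says that its examples are not exhaustive.
- **Fellow-eye Hydrus.** A reader might also infer that Section 8.8 contradicts the premise, since it allows the test device in the other eye. It does not. It describes that treatment "as part of the standard of care to the fellow eye in conjunction with planned IOL implantation", after the study eye has been treated. It is permitted, not assigned by the study.
- **No claim about washout safety is planned.** Nothing in the documents says that the trial will report washout as free of fellow-eye effects.

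None of this rescues the premise. It limits what follows from its failure.

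**Conclusion.** The point holds in a limited form. The reason given in Section 9.1 is contradicted by the protocol's own oral-drug washout, which is required at screening and applied again through Table 2 before Months 12 and 24. As a result, non-serious fellow-eye events during a study-imposed washout of a systemic agent are not captured as adverse events on the CRF, while the chart and the bilateral examinations retain part of the information.

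The number affected is unknown and may be small. The 2 to 10% range is an assumption, and the protocol is inconsistent about the number randomized (150 or 70). The primary endpoint is study-eye diurnal pressure and does not change. This is a gap in safety capture that should be corrected because correction is cheap. It is not a threat to the validity of the efficacy comparison.

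**What to change.** In Section 9.1 and on the adverse event form:

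1. Delete the statement that no aspect of the study can affect both eyes.
2. Require fellow-eye ocular adverse events of any severity to be recorded during each washout period in subjects who stop a systemic pressure-lowering drug.
3. Add medication washout to the relationship categories, and identify the eye. An eye field alone would not let an event be attributed to washout.
4. Keep the serious-only rule for the fellow eye in all other circumstances.

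Optionally, also record non-serious events in a fellow eye that receives the Hydrus. The reason would be additional device safety data, not any conflict between Sections 8.8 and 9.1.

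The cost is a short change to Section 9.1, a small change to one form, and slightly more adverse event reporting by sites. No washout period or treatment rule changes.

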# 9.2 Anticipated Adverse Events

Anticipated AEs associated with glaucoma and/or cataract surgical procedures that might reasonably be expected to occur in this study are listed below. These specific examples of anticipated AEs include, but are not limited to:

# 9.3 Intraoperative Adverse Events

Complications of cataract surgery

- Anterior capsule tear
- Posterior capsular rupture
- Vitreous in the anterior chamber
- Choroidal detachment

Other complications

- Hyphema obscuring the surgeon's view
- Choroidal hemorrhage or effusion
- Significant iris injury or trauma
- Corneal edema
- Zonular dialysis

#### 9.4 Postoperative Adverse Events

Postoperative adverse events include:

- Chronic pain in the study eye  $\geq 3$  months postoperative
- Flat anterior chamber with lens/cornea touch or with iridocorneal apposition without lens/cornea touch >1 month postoperative
- Best-corrected visual acuity loss of 2 lines (10 letters) or more on the ETDRS chart measured at or after 3 months postoperative
- Hypotony (defined as IOP < 6 mmHg) at or after 1 month postoperative
- Maculopathy including hypotonic maculopathy
- Device obstructed by iris, vitreous, lens, fibrous overgrowth, fibrin, or blood
- Device explantation
- Device malposition, dislodgement or movement
- Wound dehiscence (persistent aqueous leak or fistula formation)
- Inflammation (defined as any inflammation requiring treatment with topical, sub-Tenon's or systemic anti-inflammatory medication) lasting longer than 1 month
- Endophthalmitis
- Persistent hyphema of > 2 mm present > 1 week postoperative
- Corneal opacification
- Corneal decompensation
- Corneal edema persisting > 1 month (mild to moderate corneal edema prior to 1 month postoperative is not considered an adverse event)
- Retinal complications (flap tears, retinal detachment, or proliferative vitreoretinopathy)
- Elevated mean  $IOP \ge 10$  mmHg than the qualifying baseline mean IOP > 1 month postoperative
- Events resulting in an unplanned ocular surgical reintervention (other than paracentesis to relieve pressure prior to 1 week postoperative)
- Phthisis
- Significant foreign body sensation at or after 3 months postoperative
- A change in C/D ratio of  $\geq 0.3$  units on slit lamp biomicroscopic examination
- Peripheral anterior synechia
- A 2-point worsening to 4+ anterior chamber cells or flare at or after 3 months postoperative, not associated with a pre-existing condition
- A 2-point worsening to severe on the slit lamp examination findings (other than cells and flare) at or after 3 months postoperative not associated with a pre-existing condition
- A 2-point worsening of ocular symptoms to severe or very severe at or after 3 months postoperative not associated with a pre-existing condition

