# 5.0 STUDY ENDPOINTS

The primary effectiveness endpoint for this study is diurnal IOP at 12 months following the washout of all glaucoma medications.

Secondary effectiveness endpoints include:

- A reduction in IOP of at least 20% following the wash-out, as compared to the washed-out baseline.
- An IOP of no less than 5mmHg and no more than 18mmHg at 12 months post washout.

Safety outcomes include loss of lines of BCVA, results of slit lamp and fundus examination, and the incidence of complications and adverse events.

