#### 8.4 Perioperative Medication

A topical antibiotic and a topical steroid will be administered after surgery. The following dosing regimen is recommended:

- 1. Moxifloxacin 0.5% (Vigamox®), one drop four times per day commencing the day of the procedure and continued for one week postoperatively.
- 2. Prednisolone acetate 1.0% (Pred Forte®), one drop four times per day for one week; followed by one drop three times per day for one week; followed by one drop two times per day for one week; followed by one drop once per day for one week, then discontinue.

Medication to treat transient post-operative spikes in IOP resulting from the use of viscoelastic and surgical manipulation may be required in the immediate postoperative period.

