# 8.7 Postoperative Ocular Hypotensive Medications

Since the study population is undergoing cataract surgery involving use of an ophthalmic viscoelastic agent and post-operative steroids, both of which are known to cause IOP elevation, use of glaucoma medications in the first month after surgery is expected in some cases. In these cases, additional visits may be performed to assess IOP, and medications discontinued if the subject's condition allows.

Long-term medical therapy may be implemented or additional surgical measures may be performed at any time during the study at the Investigator's discretion in the event it is required. The primary concern of the Investigator and Sponsor at all times is the health and safety of the subjects.

A record of all medications added, discontinued or changed will be documented on the appropriate Case Report Form for each scheduled visit or on a Case Report Form for an Unscheduled (Interim) Visit, if necessary.

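### Early postoperative IOP elevation, which the protocol expects and measures, would reach the safety tables only through unstandardised adverse-event reporting

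*Combined protocol and SAP*

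**What the plan says.** **Early IOP elevation is expected.** Section 8.4 states that "Medication to treat transient post-operative spikes in IOP resulting from the use of viscoelastic and surgical manipulation may be required" soon after surgery. Section 8.7 says of viscoelastic and postoperative steroids, "both of which are known to cause IOP elevation", and adds that "use of glaucoma medications in the first month after surgery is expected in some cases".

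**It is measured.** The visit lists in 8.6 and the schedule in Appendix 1 record Goldmann IOP and ocular medications at Day 1, Week 1 and Month 1.

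**The listed IOP events start late.** In 9.4, raised IOP (10 mmHg or more above the qualifying baseline mean) is listed only beyond 1 month. The low-pressure item is "Hypotony (defined as IOP < 6 mmHg) at or after 1 month postoperative". The reintervention item is "Events resulting in an unplanned ocular surgical reintervention (other than paracentesis to relieve pressure prior to 1 week postoperative".

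**IOP is not a named safety outcome.** Section 5.0 says: "Safety outcomes include loss of lines of BCVA, results of slit lamp and fundus examination, and the incidence of complications and adverse events". Section 6.3 tabulates safety outcomes at Months 1, 3, 6, 12, 18 and 24. The Study Outline makes the safety analysis descriptive.

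**The general definition is wider.** Section 9.1 counts every ocular adverse event in the study eye, with no time limit. Section 9.2 presents the lists that follow as non-exhaustive examples. The serious-event criteria in 9.7 have no time limit either.

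**The concern.** The protocol expects a particular harm in the first month and collects the data that would show it. It then describes its IOP events so that they begin when that month is nearly over or has ended. An eye with a marked pressure rise on Day 1 meets no listed IOP item, and if the rise is relieved by paracentesis in the first week, the reintervention item does not cover it. Whether such an eye appears in any safety table then depends on how the site reads 9.1 and 9.2 against 9.4.

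At stake is the interpretability of a low or equal count of early IOP events. With up to nine sites (Study Outline) using their own judgement, the count would partly reflect reporting habit. A reader of the safety tables could not tell few early spikes from few early spikes reported. Section 8.4 attributes spikes partly to surgical manipulation, and the two arms receive different devices in the angle, so a by-arm view is of natural interest, although the documents do not predict a difference.

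**Working it through.** The point rests on setting sections side by side. Arithmetic is needed only to show what the added summary could deliver.

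**Step 1: which visits fall outside the listed IOP items.** Appendix 1 has 8 postoperative tonometry visits: Day 1, Week 1 and Months 1, 3, 6, 12, 18 and 24.
- Day 1 and Week 1 lie wholly before both the raised-IOP and the hypotony limits: 2 of 8.
- Month 1 has a window of 30 ± 7 days, that is days 23 to 37. One month is not defined in days. If it means 30 days, readings on days 23 to 29 fall short of the hypotony limit, and those on days 23 to 30 fall short of the raised-IOP limit. Month 1 is therefore partly covered.

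**Step 2: what level of pressure is involved.** The baseline paragraph in 8.6 requires a diurnal mean of 22 to 36 mmHg. Adding 10 mmHg puts the listed raised-IOP level at 32 to 46 mmHg, depending on the eye. A reading at that level on Day 1 or at Week 1 matches no listed IOP item.

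**Step 3: what other routes exist.**
- 9.1 and 9.2: an early spike may be reported at the site's judgement.
- 9.4: reinterventions other than early pressure-relieving paracentesis are listed; hypotonic maculopathy is listed without a time limit.
- 9.7: a serious early event is classified as such at any time.
- 8.7: medication changes are recorded, but no by-arm summary of them is described.

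A non-serious early spike, early low pressure without maculopathy, early drops and first-week paracentesis have no standard route into the safety tables.

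**Step 4: precision of a by-arm summary.** Inputs are n = 75 per arm (6.2) and assumed common event rates p, since the documents give none.

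Half-width of the 95% interval for a difference = 1.96 × √(2p(1 − p)/n)
- p = 5%: 1.96 × √(0.095/75) = 7.0 points
- p = 10%: 1.96 × √(0.18/75) = 9.6 points
- p = 20%: 1.96 × √(0.32/75) = 12.8 points

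Section 8.1 gives a randomised population of 70, which conflicts with about 150 in 4.0 and needs separate reconciliation. At 35 per arm the half-widths would be 10.2, 14.1 and 18.7 points.

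**Step 5: power, to show why a test is not proposed.** Two-sided 5% level (assumed), n = 75 per arm, p̄ the mean of the two rates:

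Power = Φ{[|p₁ − p₂| − 1.96√(2p̄(1 − p̄)/n)] / √([p₁(1 − p₁) + p₂(1 − p₂)]/n)}
- 10% v 20%: Φ[(0.100 − 0.114)/0.0577] = 0.40
- 5% v 15%: 0.53
- 5% v 20%: 0.80
- 10% v 30%: 0.87

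Only large differences would be detected with usual power.

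**The case against.** The strongest reply is that the protocol does not exclude early IOP events. Section 9.1 requires ocular adverse events in the study eye to be reported, 9.2 says the list is not exhaustive, and where 9.4 means to remove an early finding it says so: mild to moderate corneal edema before 1 month is expressly declared not to be an adverse event. There is no such sentence for IOP. This stands. A reader might infer that first-month IOP extremes are barred from adverse-event reporting; the documents do not support that. The corneal edema wording also cuts the other way, because it shows sites one meaning that a time limit in this list can carry. Section 9.0 adds that not every untoward event goes on the case report forms. The result is ambiguity.

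A reader might also infer that early IOP is singled out by not being compared between devices. It is not: safety is descriptive throughout, and a reported early event can still enter the Month 1 tabulation. Nor do the documents show that one device causes more early spikes. They give no comparison of device size and no procedural steps for the iStent; 8.4 and 8.7 cite causes common to both arms.

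Finally, the statistical sections are visibly incomplete in the public text (6.1 breaks off mid-sentence), and the 5.0 wording is open-ended. A fuller safety plan may exist. That limits the point to what can be read, but the 9.4 time limits and the paracentesis exception are stated rules, not gaps.

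**Conclusion.** The point holds in a limited form. The readable plan gives an expected early harm no standard place in the safety tables: the listed IOP events start at about 1 month, first-week pressure-relieving paracentesis is excepted, IOP is not a named safety outcome, and tabulation starts at Month 1. Two of 8 postoperative IOP visits lie wholly, and a third partly, before the listed limits. What is affected is the reporting of non-serious early IOP events and their treatment; Month 1 hypotony, other unplanned reinterventions and serious events remain captured. The primary endpoint is untouched.

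This rests on the public text being complete on safety tabulation, and on sites being able to read the 9.4 limits as reporting limits. The precision figures rest on assumed event rates and illustrate what a summary could show; they do not predict a device difference.

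**What to change.** 1. In 5.0 and 6.3, add a descriptive summary by arm, with 95% confidence intervals for the differences and no tests, covering:
   - study-eye IOP at Day 1, Week 1 and Month 1, with the number of missing readings;
   - the proportion of eyes beyond the protocol's own 9.4 IOP thresholds at each of these visits;
   - the proportion on hypotensive medication at each visit;
   - early pressure-relieving paracentesis.
2. Label the threshold rows as single-visit readings set against a washed-out diurnal baseline mean, and as a reporting summary rather than a new adverse-event definition. The 9.4 raised-IOP item refers to a mean IOP, and early readings may be on medication, so these rows should sit beside the medication row.
3. Use a score-type interval for the proportions. At a 5% rate only about 75 × 0.05 = 3.75 events per arm are expected, where the simple normal interval is rough.
4. Confirm that early paracentesis is recorded on the interim case report form. No visit list in 8.6 names it, so it cannot be assumed to be in the data.
5. Reconcile 9.1 and 9.2 with 9.4 on whether first-month IOP events are reported as adverse events, and define 1 month in days for the Month 1 window. Which way to settle this is for the sponsor; clinical handling need not change.

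The IOP and medication rows need no new visit or measurement. The cost is a few table rows, the paracentesis check, and probably a slightly less favourable reported safety profile.

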# **1.0 INTRODUCTION AND RATIONALE**

Glaucoma is a collection of disorders characterized by progressive loss of visual fields due to optic nerve damage, and is the leading cause of blindness in the U.S., affecting 1-2% of individuals aged 60 and over. Research has determined that the rate of primary open-angle glaucoma (POAG) – the most common form of glaucoma -- in the United States is at 2.2 million people. Based on that figure, it is estimated that between three and six million people in Europe, and approximately 3 million people in South America have elevated intraocular pressure and are at an increased risk for developing POAG. POAG accounts for 90% of all cases of glaucoma. It is a slow, progressive disease that produces no symptoms in its early stages. Although the drainage system of the eye remains open and functions properly, the eye is unable to remove the excess fluid at a pace sufficient to prevent a rise in intraocular pressure (IOP). Progressive vision loss tends to be painless, and subjects often present with advanced disease.

Although there are many risk factors associated with the development of glaucoma (age, race, myopia, family history, and injury), elevated intraocular pressure is the only risk factor that can be successfully treated and that is correlated with the reduction of glaucomatous optic neuropathy. Management of glaucoma requires chronic, lifelong treatment with a spectrum of therapeutic options including medications, laser treatment and microsurgical devices / implants, all with the therapeutic goal of lowering intraocular pressure to target levels in order to prevent loss of visual fields from excessive pressure on the optic nerve.

Historically, first-line treatment for elevated intraocular pressure consists of medical therapy. Results of the Early Manifest Glaucoma Trial (EMGT), the Advanced Glaucoma Intervention Study (AGIS), the Collaborative Initial Glaucoma Treatment Study (CIGTS), the Normal Tension Glaucoma Study (NTG), and the Ocular Hypertension Treatment Study (OHTS) indicate that topical ocular hypotensive medication is effective in reducing intraocular pressure and thus delaying or preventing the progression of POAG.

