# 3 Months Postoperative (90 $\pm$ 14 days)

The following information will be captured for the study eye at this visit:

- Ocular medications
- Manifest refraction
- ETDRS BCVA
- Humphrey 24-2 SITA standard visual field
- Slit lamp biomicroscopy
- Goldmann tonometry at 8:00 AM  $\pm$  1 hour
- Fundus examination and C:D ratio assessment
- Gonioscopy
- Adverse events

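### Section 9.4 counts a C/D change of 0.3 or more as an adverse event without giving a direction or reference visit, so a smaller cup can be reported as harm and sites may count differently

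*Combined protocol and SAP*

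**What the plan says.** Section 9.4 includes "A change in C/D ratio of $\geq 0.3$ units on slit lamp biomicroscopic examination" in its list of postoperative adverse events. The item gives no direction, reference visit, time window or confirmatory reading.

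Other items in that list that compare an eye with an earlier state do give a direction: "Best-corrected visual acuity loss of 2 lines (10 letters) or more on the ETDRS chart", "A 2-point worsening to 4+ anterior chamber cells or flare at or after 3 months postoperative", two further 2-point worsening items, and mean IOP elevated relative to the qualifying baseline.

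Section 9.1 sets the reporting rule: "Adverse events as defined in this protocol include all ocular adverse events (AE) in the study eye". It asks the investigator to categorize each event by degree of harm. It also says that changes in a chronic condition consistent with natural progression are not adverse events.

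C/D ratio is read once before surgery, at Screening (Section 8.6 and Appendix 1), in eyes with an operable cataract and BCVA of 20/40 or worse (Section 7.1). It is read again at Months 3, 6, 12, 18 and 24; the Month 3 entry, for example, is "Fundus examination and C:D ratio assessment". Section 5.0 names the incidence of adverse events as a safety outcome, and Section 6.3 plans frequency tabulations of safety outcomes.

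**The concern.** Section 1.0 describes glaucoma as "progressive loss of visual fields due to optic nerve damage". The disc sign of that harm is an enlarging cup, and a smaller cup does not show it. Yet the event is worded "A change in C/D ratio of" 0.3 units or more, so on the ordinary reading a cup going from 0.8 to 0.5 is reported in the same way as one going from 0.5 to 0.8.

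At stake is what the disc line of the safety table means. Decreases counted as events add entries that carry no information on disc damage. If some sites report decreases and others do not, the count also depends on who read the rule. Five postoperative readings against a single preoperative one give reading error five chances to cross the limit, and no confirmation is asked for.

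**Working it through.** **1. The text.** The plan states no rate for this event, so there is no figure to reproduce. The passages compare as follows.

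| Item or clause | Direction stated? |
|---|---|
| 9.4 acuity | yes, loss |
| 9.4 mean IOP | yes, elevated, against the qualifying baseline |
| 9.4 2-point items (three) | yes, worsening |
| 9.4 C/D ratio | no, and no reference visit |
| 9.1 reporting rule, 6.3 tabulation | neither limits or splits C/D events by direction |
| 9.1 natural-progression clause | can remove an enlarging cup from the count, but not a shrinking one |

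**2. Share of noise-only events that are decreases.** Let two readings of an unchanged cup have independent errors with the same SD s. Their difference is symmetric about 0 with SD s√2, so

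P(up) = P(down) = 1 − Φ(0.3 / (s√2)).

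Half of the events are decreases, whatever s is. For one comparison at s = 0.10: 0.3 / 0.1414 = 2.12, so P(up) = 1.7% and P(either) = 3.4%. In 150 subjects that is 5.1 events as written against 2.5 for increases only. Simulation with readings rounded to 0.1 and limited to 0–1 gives a decrease share of 49.7% to 50.3% for s from 0.075 to 0.15 and true cups from 0.5 to 0.9.

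**3. Subjects flagged at least once over five visits.** From the documents: one Screening reading, five postoperative readings, and about 150 randomized subjects (Section 4.0; Section 8.1 gives 70, which would scale the counts but not the percentages). Assumed: no true change, true cup uniform from 0.4 to 0.8, normal independent errors, and readings to the nearest 0.1. The SD is an assumption because the documents give none.

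| Reading SD | As written | Increases only | Subjects of 150 |
|---|---|---|---|
| 0.05 | 0.45% | 0.22% | 0.7 against 0.3 |
| 0.08 | 12% | 6% | 18 against 9 |
| 0.10 | 28% | 14% | 42 against 21 |

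**4. What moves these figures.**

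- *Systematic shift m between preoperative and postoperative readings.* P(up) = 1 − Φ((0.3 − m)/(s√2)) and P(down) = Φ((−0.3 − m)/(s√2)). For one comparison at s = 0.10 and m = −0.05, P(up) = 0.67% and P(down) = 3.85%, so decreases are 3.85 / 4.52 = 85% of events. At m = +0.05 they are 15%. In the five-visit model at SD 0.08 the shares are about 87% and 13%.
- *Error that persists within an eye.* If half the error variance is stable within an eye (an assumption), SD 0.08 gives 1.4% against 0.7%, about 2 against 1 of 150 subjects.

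**The case against.** The strongest reply is that the text never says absolute change or either direction. Read as follow-up minus baseline, 0.8 to 0.5 is −0.3 and does not meet the limit. Section 9.2 introduces its lists as examples, Section 9.0 speaks of untoward events, and Section 9.1 asks for a grade of harm, so an investigator who sees an improved cup has nothing to grade. No automatic scoring rule appears in the documents. All of this stands as a reason why some sites would not make the error. None of it states a direction, though, so the count becomes dependent on the site rather than correct.

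A reader might also infer more than the documents support:

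- *That the rule certainly scores absolute change.* This is the ordinary reading, but a signed reading is possible.
- *That half of false events point the wrong way in this trial.* That needs equal, symmetric errors before and after surgery. The Screening reading is taken before cataract removal. The fundus examination is specified as dilated at Screening and Months 12, 18 and 24, but not at Months 3 and 6. A shift in either direction is therefore possible.
- *That 18 against 9 is the expected count.* It is one point in a range that starts below 1 of 150 subjects.
- *That the wording dilutes a device difference or penalises the device that lowers IOP more.* Section 6.3 plans only tabulations, and no passage says that cups shrink by 0.3 or do so differently by device.

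C/D is recorded at each of these visits, so the direction of change can be recovered from the collected data.

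**Conclusion.** The item is wrong as written, and the severity is minor. Section 9.4 leaves out the direction that comparable items carry, and no other section supplies it. A cup measured 0.3 smaller can therefore enter a named safety outcome as harm, and sites may differ on whether it does.

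Under symmetric, equal errors, about half of noise-only events are decreases; a systematic shift moves that share up or down. With independent errors, the number flagged over five visits runs from under 1 of 150 subjects at SD 0.05 to about 42 as written against 21 at SD 0.10, and within-eye persistence lowers it. Primary and secondary endpoints are untouched. The effect is confined to one line of a descriptive safety tabulation.

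**What to change.** In Section 9.4, reword the item as an increase in C/D ratio of 0.3 units or more from the Screening value. Tabulate decreases of 0.3 or more descriptively, outside the adverse event counts. Reconcile the item with the Section 9.1 clause on natural disease progression, since that clause can remove an enlarging cup, which is the event the item should capture.

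The cost is a short text change in Sections 9.4 and 9.1, with matching CRF instructions to the sites. No extra visit or measurement is needed. Under symmetric errors the noise-only count halves; with a shift in readings the reduction would be larger or smaller.
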